3.1 Study Rationale

Relapsed/Refractory Diffuse Large B Cell Lymphoma (DLBCL) has a dismal prognosis, especially with relapse/refractory disease after autologous stem cell transplantation. Recently, a new adoptive cell transfer therapy, CAR-T cells, that manufactures a patient's T cells to express artificial receptors on their cell surface has shown promising results in patients that relapse or have refractory disease. However, there are subset of patients that fail to manufacture a sufficient amount of CAR-T cells ex vivo, have poor expansion in vivo or lose persistence of their CAR-T cells after infusion. This has been attributed to relapsed/refractory DLBCL patients having a predominance of more differentiated T cells that are senescent and have poor expansion potential for CAR-T cell manufacturing. This pilot study will examine if a 2-week exposure to Duvelisib, will favorably change a patient's T cell phenotype for manufacturing of more potent CAR-T cells for relapsed/refractory DLBCL and relapsed/refractory follicularlymphoma patient receiving commercial tisagenlecleucel.

3.2 Clinical Experience

3.2.1 Pre-Clinical Studies

Based upon this rationale, a series of preclinical studies involving *ex vivo* culture of mononuclear cells from healthy volunteers and patients with DLBCL, we showed that the addition of duvelisib, an FDA-approved PI3K delta and gamma inhibitor, significantly augmented overall expansion of T-cells from healthy donors and DLBCL patients.¹⁶ Phenotypic analysis of these cells revealed increased frequencies of non-senescent, naïve and memory T-cells that express both CD27 and CD28.¹⁶ Duvelisib enhanced expansion of T cells from patients with DLBCL, while increasing expression of co-stimulatory molecules. More recently, we have shown that incubation with pharmacologically achievable and clinically relevant doses of duvelisib recapitulated the effect of duvelisib on T-cell expansion in healthy donors and patients with CLL (Funk et al., SITC 2019; unpublished data). To assess the influence of PI3K delta and gamma inhibitor during *ex vivo* T cell culture, dose-response experiments of duvelisib or idelalisib (PI3K delta inhibitor) assessing the influence of these drugs upon T cell number and quality across logarithmic scales revealed a dose-dependent increase in the frequency of both CD8 positive T-cells and CD3 positive but CD4 negative CD8 negative cells, with corresponding decreases in CD4 cells (Funk et al., SITC 2019;unpublished data). These differences in the ratios of these T cells are particularly observed at doses of PI3K inhibitor sufficient to inhibit both PI3K delta and gamma. In a survey of the literature, Stock et al. (2019) reported a similar observations in that the ratio of CD8:CD4 T cells from patients with CLL increased when cultured with 1 μ M idelalisib, such that ratios of CD8:CD4 T cells became more similar to those observed T cells cultured from healthy volunteers.³³ Of note, 1 μ M idelalisib is sufficient to inhibit both

Protocol Title: Duvelisib Exposure to Enhance Immune Profiles of T Cells in Patients with Diffuse Large B Cell Lymphoma (DEEP T CELLS)

PI3K delta and gamma, but idelalisib cannot be administered at doses that achieve drug levels sufficient to inhibit PI3K gamma. Further analysis of the CD3 positive CD4 negative CD8 negative subset revealed that duvelisib (and idelalisib) significantly increase absolute numbers of Gamma Delta T-cells following 10 to 15-day *ex vivo* culture, particularly at doses sufficient to inhibit both PI3K delta and gamma (unpublished data). The T-cells expanded with a PI3K delta inhibitor (idelalisib) have improved survival following transfer to NSG mice as well as enhanced cytotoxicity against lymphoma targets using human and murine preclinical model systems.¹⁶

In summary, a body of preclinical literature and data suggest that modulation of the PI3K pathway, utilizing duvelisib, an isoform-selective inhibitor of PI3K delta and gamma, represents a strategy with potential to enhance the phenotype and expansion of T cells from patients with DLBCL and relapsed/refractory follicular lymphoma, which may enhance CAR T cell mediated outcomes. In an effort to translate these preclinical observations to the clinic, we hypothesize that 8 to 15 days of duvelisib exposure in patients with DLBCL or relapsed/refractory follicular lymphoma will enhance frequencies of T cells with replicative potential, so that mononuclear apheresis product collected for CAR-T manufacture following duvelisib exposure will result in faster manufacturing time than historical controls. We predict that one benefit of a reduced manufacture duration will be enhanced viability of the final CAR T cell product. Further, we hypothesize the enhanced yield of metabolically fit T cells will lead to generation of CAR T cells that will exhibit enhanced *in vivo* persistence and proliferation, significant since these factors are associated with longer remissions. Further, we predict infusion of CAR-T-cell product generated from patients pre-treated with duvelisib will not result in significantly different levels of CRS or neurotoxicity compared to patients treated with CAR-T-cells manufactured from a mononuclear cell apheresis product collected without prior exposure to PI3K inhibitors.

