1.1 Synopsis

This pilot study will evaluate a 8 to 15 day exposure to duvelisib in patients with relapsed/refractory Diffuse Large B Cell Lymphoma (DLBCL) or follicular lymphoma prior to undergoing apheresis of a mononuclear cell product for the purpose of CAR-T manufacturing. The primary objective of the study is to determine whether the immune profile of T cells can be favorably changed by short-term exposure to duvelisib prior to collection of mononuclear cells for CAR-T 19 cell manufacturing. Secondary objectives include feasibility of adherence to duvelisib for 8 to 15 day, assessment of manufacturing time of patients, assessment of proportions of CD27/CD28 T cells and CD4/CD8 double negative Gamma Delta T cells to historical controls, comparison of rates cytokine release syndrome (CRS)neurotoxicity or ICU transfer and overall response rate (ORR) at 90 days. The study will also determine if a 8 to 15 day exposure to duvelisib is safe and well tolerated in this setting.

Title:	Duvelisib Exposure to Enhance Immune Profiles of T Cells in Patients with Diffuse Large B Cell Lymphoma (DEEP T CELLS)
Study Description:	
This Pilot study will evaluate whether an 8 to 15 day exposure to Duvelisib will favorably change the immune profile of T cells prior to CAR-T 19 cell manufacturing. We hypothesize that short term exposure to Duvelisib will:
 
increase frequencies of CD27/28 double positive naïve and memory T cells.increase frequencies of CD8+CD45RO-CD27+ T cells.increase frequencies of CD4/CD8 double negative Gamma Delta T cells.
Objectives:	
Primary Objective:
 
To assess changes in T cell phenotype after 8 to 15 day exposure to duvelisib prior to collection of mononuclear cells for CAR-T cell manufacturing. 
Secondary Objectives:
 
To evaluate compliance with duvelisibTo evaluate the CAR-T 19 manufacturing timeTo describe frequencies of CD27/28 double positive T cells and CD4/8 double negative T cellsTo evaluate expansion and persistence of CAR-T cellsTo evaluate overall response rates following CAR-T cell therapyTo evaluate survival rates following CAR-T cell therapyTo describe the frequency of CRS and neurotoxicity requiring ICU transfer (for CRS or neurotoxicity) and/or treatmentDescribe the safety and tolerability profile of duvelisib

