17.5.3 Analysis of Secondary Endpoints

- 1). Descriptive statistics will be used to calculate the proportion of patients that completed at least 75% of duvelisib doses as documented by the patient pill diaries. The proportion along with an exact 95% confidence interval will be reported.
- 2). Descriptive statistics will be used to calculate the median manufacturing time from the 10 patients that completed at least 75% of duvelisib doses. The median will be reported along with the minimum and maximum manufacturing times.
- 3). A Wilcoxon signed-rank test will evaluate the change in proportion of CD27+/CD28+ and CD4-/CD8- T cells at baseline and at day 15
- 4). Descriptive statistics will be used to calculate the *in vivo* expansion and persistence of CAR-T 19 cells post infusion as measured by serial CAR-T 19 PCR measurements.
- 5). The ORR (complete response or partial response) will be summarized along with an exact 95% confidence interval. Disease response will be based on the RECIST criteria (version 1.1). Please see section 8.2 on the definitions of disease response.

6). The 90 day PFS and OS will be estimated using the Kaplan-Meier method and calculated with corresponding 95% confidence intervals. Please see section 8.3 on the definitions of progressive disease.

7). Descriptive statistics will be used to calculate the frequency of ICU transfers due to CRS and/or neurotoxicity. Descriptive statistics will also be used to calculate the frequency of administration of tocilizumab and/or corticosteroids use for CRS and/or neurotoxicity.

8). Descriptive statistics will be used to assess the frequency of all grade toxicities as defined by CTCAE (version 5.0).

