17.5.5 Safety Analysis

Adverse event data will be described and graded per the NCI CTCAE 5.0 guidelines. For each adverse event, information to be collected includes event description, time of onset, clinician assessment of severity, relationship to study product (assessed only by those with the training and authority to make a diagnosis), current correlate laboratory values (regardless of hematologic or non-hematologic etiology), treatment of AE and time of resolution/stabilization of the event. Regardless of relationship, all AEs will be recorded with start dates occurring any time after patient receives any duvelisib. At each study visit, the investigator will inquire about the occurrence of AE/SAEs since the last visit. Events will be followed for outcome information until resolution or stabilization.

Any medical condition that is present at the time that the participant is screened will be considered as baseline and not reported as an AE. However, if the study participant's condition deteriorates at any time during the study, it will be recorded as an AE. Changes in the severity of an AE will be documented to allow an assessment of the duration of the event at each level of severity to be performed. AEs characterized as intermittent require documentation of onset and duration of each episode.

Protocol Title: Duvelisib Exposure to Enhance Immune Profiles of T Cells in Patients with Diffuse Large B Cell Lymphoma (DEEP T CELLS)

The maximum grade for each type of toxicity will be recorded for each patient, and frequency tables will be reviewed to determine toxicity patterns. Adverse events will be summarized and described within each cohort. They will initially be reviewed regardless of attribution, but also whether they are possibly, probably, or definitely related to treatment. In addition, we will review all adverse event data that are graded as 3, 4, or 5 and classified as either "unrelated" or "unlikely to be related" to study treatment in the event of an actual relationship developing. The incidence of severe adverse events or toxicities will be described. We will assess the proportion of patients who experience grade 3 or higher non-hematologic toxicity. To assess tolerability, we will also capture the proportion of patients who go off treatment due to adverse events.

17.6 Data/Specimens:

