Due to possible increased potency and increased toxicity risk-profile of tisagenlecleucel manufactured from the mononuclear cell apheresis product collected following treatment with duvelisib, all SAE that are collected will be reported to Novartis within 24 hours according to the following Table:

Interventional Clinical Trial WITH Tisagenlecleucel	
Collection by Sponsor	Transfer to Novartis

• All SAEs• All non-serious AEs• All reports of drug exposure during pregnancy and pregnancy outcome. Pregnancy and pregnancy outcome should also be collected for the female partner of any male patient who was treated with tisagenlecleucel, provided consent has been obtained from the female partner.• All reports of abuse and misuse of an investigational medicinal product, other medication errors and uses outside of what is foreseen in the protocol (irrespective if a clinical event has occurred).	
Within 24 hours of awareness, transfer the following safety events:
 
• All collected SAEs in patients exposed to tisagenlecleucel• All collected reports of tisagenlecleucel exposure during pregnancy and pregnancy outcome. All collected reports of pregnancy and pregnancy outcome of the female partner of any male patient who was treated with tisagenlecleucel, provided consent has been obtained from the female partner.• All collected reports of abuse and misuse of tisagenlecleucel.

In particular, any episode of CRS or neurotoxicity grade 2 or greater observed within the first 100 days after tisagenlecleucel infusion will be reported to Novartis.

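### The safety endpoints are planned as bare frequencies without confidence limits, so 20 patients cannot support the protocol's statements about safety or similar CRS and neurotoxicity

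*Combined protocol and SAP*

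**What the plan says.** Three places speak to what the trial will show about safety.

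- Synopsis, section 1.1: "The study will also determine if a 8 to 15 day exposure to duvelisib is safe and well tolerated in this setting". The same paragraph lists, among the secondary objectives, a "comparison of rates cytokine release syndrome (CRS)neurotoxicity or ICU transfer".
- Section 3.2.1: a prediction that the product "will not result in significantly different levels of CRS or neurotoxicity compared to patients treated with CAR-T-cells" that were "manufactured from a mononuclear cell apheresis product collected without prior exposure to PI3K inhibitors".
- Section 18.4 gives the reason for expedited reporting to the cell manufacturer: "Due to possible increased potency and increased toxicity risk-profile of tisagenlecleucel manufactured from the mononuclear cell apheresis product" collected after duvelisib.

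The planned analyses are thinner. Section 17.5.3, item 7: "Descriptive statistics will be used to calculate the frequency of ICU transfers due to CRS and/or neurotoxicity"; tocilizumab and corticosteroid use is handled the same way, and item 8 gives toxicities as frequencies. Section 17.5.5: "We will assess the proportion of patients who experience grade 3 or higher non-hematologic toxicity"; stopping treatment because of adverse events is also a plain proportion.

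Other endpoints in the same list are treated differently. Item 5: "The ORR (complete response or partial response) will be summarized along with an exact 95% confidence interval". Item 1 (adherence) also has an exact 95% interval, and item 6 (PFS and OS) has 95% intervals.

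For CRS, neurotoxicity and toxicity the documents give no test, alpha, margin, acceptable rate, reference rate or named historical cohort.

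**The concern.** The protocol sets out to say something about safety and about similarity to unexposed CAR-T patients, and it recognises that the product might be more toxic. The endpoints that bear on this are the ones reported without any measure of uncertainty. A report of 2 of 20 (10%) ICU transfers would meet the plan as written, and nothing in the plan would make the reader see that a rate of 30% is not excluded.

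The wording in 3.2.1 adds a second difficulty. A lack of significant difference is a weak standard in a sample of 20, because it is easily met when harm is real. If the final report relied on it, the prediction could be called confirmed by data that are compatible with a material excess.

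**Working it through.** **Inputs from the documents.** 20 patients, single arm (1.1, 5.1, 17.5.2). The sample size carries no power or precision calculation, and 17.5.2 describes the trial as based on estimation. There is therefore no planned safety figure to reproduce.

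**Inputs assumed.** The documents give no background rate for ICU transfer, tocilizumab or corticosteroid use, or grade 3 or higher toxicity. Rates from 5% to 40% are used below as a range. The 5% significance level is also an assumption.

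**Step 1: what 20 patients can exclude.** This needs no background rate and no test. The Clopper-Pearson 95% upper limit for x events in n patients is the 97.5th percentile of a Beta(x+1, n−x) distribution. For x = 0 it is 1 − 0.025^(1/n), so for n = 20 it is 1 − 0.025^(0.05) = 16.8%.

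| Events of 20 | Observed | Exact 95% upper limit |
|---|---|---|
| 0 | 0% | 16.8% |
| 1 | 5% | 24.9% |
| 2 | 10% | 31.7% |
| 3 | 15% | 37.9% |
| 4 | 20% | 43.7% |

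From 1 to 4 events the upper limit is more than twice the observed rate (for 4 events, 43.7/20 = 2.2 times).

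The denominator for CAR-T events may be below 20, because some patients may not be infused. If 16 were infused (assumed), 0 events would leave 20.6% not excluded; if 15 (assumed), 0 events would leave 21.8% and 2 events 40.5%.

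**Step 2: what a non-significant result would mean, if someone relied on one.** Take an exact two-sided 5% binomial test of n = 20 against a fixed rate p0. Let r be the smallest count above expectation with p ≤ 0.05. The chance of missing a true doubling is P(X ≤ r − 1) for X ~ Binomial(20, 2·p0).

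| p0 → true rate | r | Doubling missed |
|---|---|---|
| 5% → 10% | 4 | 87% |
| 10% → 20% | 5 | 63% |
| 15% → 30% | 7 | 61% |
| 20% → 40% | 8 | 42% |
| 25% → 50% | 10 | 41% |
| 30% → 60% | 11 | 24.5% |
| 35% → 70% | 12 | 11% |
| 40% → 80% | 13 | 3% |

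With a one-sided 2.5% test the figures at 10% and 20% rise to 80% and 60%; the other rows do not change.

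Against a historical cohort instead of a fixed rate (Fisher exact, two-sided 5%), a doubling from 20% to 40% is missed in 81% of trials with 20 controls and in 57% with 100. From 30% to 60% it is missed in 65% and 32% respectively.

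**Reading the two steps together.** Up to a background rate of about 15%, a doubling is missed more often than not under every variant above. At 20% the answer depends on the test. At 25% and above, against a fixed rate, a doubling is detected more often than missed. The interval argument in step 1 holds whatever the background rate is.

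**The case against.** The strongest reply is that the plan never commits to the inference at issue. The sentence in 3.2.1 is a prediction in a background section. The listed secondary objective (1.1 and 2) is to describe the frequency of these events, and 17.5.3 is descriptive. Low power for secondary safety events is normal in a 20-patient pilot. Safety is also overseen in other ways: expedited reporting of serious events, reporting of grade 2 or higher CRS and neurotoxicity within 100 days, review of adverse events regardless of attribution, and monitoring committee review (17.5.5, 18.4, 18.6). Finally, anyone can compute an exact interval from a count and a denominator.

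Much of this stands. A reader might infer that a doubling of severe events would usually be read as safe. The documents do not support that. They contain no significance test for these endpoints and no rule that non-significance means safety. Item 7 counts ICU transfers and tocilizumab or corticosteroid use, not graded severe events. And step 2 does not bear out usually missed once the background rate is above about 15 to 20%.

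What the reply does not answer is the mismatch inside the document. A descriptive, estimation-based pilot is where intervals belong, and the plan already gives them to adherence, ORR, PFS and OS. The oversight provisions deal with individual events and trial conduct; they put no bound on the final safety statement. The synopsis still says that the study will determine safety.

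**Conclusion.** The point holds as a gap in estimation and wording. The documents promise a determination of safety, mention a comparison of CRS and neurotoxicity rates and predict no significant difference, but plan no interval for the endpoints concerned. With 20 patients even zero events leaves rates up to 16.8% not excluded, and 2 events leave rates up to 31.7%. These limits rest only on the number of patients.

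The added statement that a non-significant result would miss a doubling in roughly 60 to 90% of trials applies to a fixed reference rate of about 15% or lower, and that rate is an assumption. At 30% the figure is about 25%, and at 35% about 11%.

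This is a cheap improvement to the plan. It does not show that the trial would reach a wrong conclusion about safety.

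**What to change.** 1. In 17.5.3 items 7 and 8 and in 17.5.5, report these proportions with exact (Clopper-Pearson) 95% confidence intervals: ICU transfer for CRS or neurotoxicity, tocilizumab or corticosteroid use, grade 3 or higher non-hematologic toxicity, and stopping treatment because of adverse events.
2. State the denominators: all infused patients for CAR-T events, and all duvelisib-exposed patients for duvelisib events. The latter agrees with 17.5.1, which makes every exposed patient evaluable for toxicity.
3. Base the safety statement on the upper limit.
4. In 1.1 and 3.2.1, word the safety aim as estimation of rates, and add that a non-significant difference will not be taken as evidence of similar toxicity.

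The cost is a few sentences and a few intervals from data already collected, with no added patients or procedures. The downside is that the safety statement becomes visibly less certain. Naming a historical comparator alone would not do the same job, since it would not show which rates the trial has excluded.

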3.2.2 Pre-Clinical Pharmacology of Duvelisib and T Cell Expansion

Duvelisib is a highly potent dual PI3K delta and gamma inhibitor with a whole blood IC₅₀ of 0.4 μ M for inhibition of the delta subunit and whole blood IC₅₀ of 1.6 μ M for inhibition of the gamma subunit (Pachter & Weaver, SITC 2018). We have seen optimal T cell expansion at duvelisib concentrations of 40nM to 0.4 μ M at 14 days.

3.2.3 PI3K Inhibitors in Clinical Settings

PI3 kinase (PI3K) inhibitors are FDA-approved for treatment of relapsed follicular lymphoma (FL) and chronic lymphocytic leukemia/small lymphocytic lymphoma (CLL/SLL). Orally bioavailable drugs are typically dosed once or twice a day with the goal of inhibiting signaling through the PI3K-AKT pathway causing reduction in the growth of malignant lymphoma cells and induction of apoptosis. PI3K inhibitors are generally well tolerated and can be given for weeks to months as continuous therapy without significant hematological toxicity. One common feature of treatment with PI3K inhibitors is the development of late autoimmune disease, including colitis, pneumonitis and rash, by blockade of differentiation into regulatory T cells which are necessary for self-tolerance and down-regulation.³⁴

4. Study Intervention/Investigational Agent

4.1 Description

4.1.1 Duvelisib

Protocol Title: Duvelisib Exposure to Enhance Immune Profiles of T Cells in Patients with Diffuse Large B Cell Lymphoma (DEEP T CELLS)

Duvelisib is an oral PI3K inhibitor. FDA approved duvelisib (Copiktra, IPI-145) on September 24, 2018. Duvelisib is approved for the treatment of adult patients with relapsed or refractory chronic lymphocytic leukemia/small lymphocytic lymphoma (CLL/SLL) after at least two prior systemic therapies, and relapsed or refractory follicular lymphoma (FL) after at least two prior systemic therapies. Refer to the approved labeling for more details on specific indications and for detailed information on duvelisib.

